Protocol NX-31380

Cover Sheet

Official Title: Boost Study 31380 (mHealth)

ClinicalTrials.gov ID (NCT number): NCT05757453

Document Date: March 30, 2022

Document Description: Protocol (Precis)

Confidentiality Statement

This document contains confidential and proprietary information of sponsor NXTech Inc, provided solely for the purpose of reviewing or performing this study under compliance of federal reporting requirements; and is not intended as public disclosure or other dissemination activity which may in any way limit intellectual property rights assertions by the sponsor.

Practices Statement

This study is to be performed in full compliance with the protocol and applicable oversight body and regulatory requirements. All required study documentation and data will be archived in accordance with preauthorized policies and procedures.

1. Background

Opioid use disorder (OUD) affects an estimated 1.9 million people in the United States (2014) with an estimated 586,000 of cases related to heroin use, and with all patients suffering harms as a result of this chronic condition. The economic impact of illicit prescription opioid abuse alone is estimated to be \$53-\$72 billion, imposing high costs to society as a whole. In previous work, NXTech developed an mHealth application derived from cognitive science findings to assist in symptom management for OUD. In this study we provide mHealth-based exercises to individuals diagnosed and in treatment for opioid use disorder to inform design of optimal mHealth (mobile healthcare) interventions for OUD.

2. Protocol and Procedures

This study consists of a feasibility study of the mHealth platform for cognitive training completion in a single-arm study of individuals in supervised treatment at the site of recruitment, under the care of an independent clinical provider.

Participants in this study of the mHealth platform (see SAP for recruitment targets) will be invited to participate by study investigators, in a local study of 8 week duration, with an optional extension of up to 8 additional weeks upon participant election.

IRB approval will be obtained by the local host institution prior to any human participants activities. Procedures are intended to adhere to the Good Clinical Practices Consolidated Guideline and the Declaration of Helsinki. Monitoring data and safety of participants will be performed by the Principal Investigator and an applicable human participants Institutional Review Board (IRB) with authorized recognition of the IRB by the study site. All participants must provide informed consent in writing before enrollment and will be informed that they may disenroll at any time. There is no more than minimal risk expected to participants in the study.

In this study, participants are requested engage with mHealth platform interactions for the duration of the study period of at least 8 weeks, in addition to completing weekly assessments. Enrollment criteria are provided in Section 3. Participants supply their own standard electronic mobile device to complete the study or may receive a loaner device. All mobile devices used in this study will be standard commercial units.

After completion of the final day of participation by the final participant, full analysis of recorded data will be completed. During the study period, intervention feasibility will be assessed using measures of utilization, in addition to structured and open-ended user feedback. Primary outcome measures are user acceptability of the and secondarily for treatment-related effects of the mHealth application as an addition to usual care.

3. Recruitment and Enrollment

Recruitment will proceed under the supervision of a local site investigator, such that participants will be offered study participation after provision of written informed consent. Participants will only be tracked by an assigned numeric ID that is unassociated with an individual's personally-identifiable information.

Patient enrollment will follow, over an up to 4 month period and participants will continue into the study in rolling fashion. Individuals will be remunerated for their participation at a rate of up to \$50 per week for the primary study period of 8 weeks (or as adjusted based on prevalent rates at the time of study execution).

Demography of enrolled participants will be collected for review during the analysis phase.

Inclusion Criteria are as follows, in addition to concurrent enrollment in a clinician-supervised treatment program:

Age 18-65 years

Diagnosis of opioid use disorder

Experiencing symptoms multiple times per week

Familiar with smartphone usage

Exclusion Criteria: None if qualified under Inclusion Criteria

4. Compliance Procedures

This study will be performed in accordance with Protocol requirements and applicable oversight body policies.

Data collection will be primarily in electronic format. All required study documentation and data records will be archived in accordance with preauthorized policies and procedures. Investigators will assure that either a waiver of consent is granted under IRB approval, or that informed consent is obtained prior to performing any research procedures. Investigators will ensure that all participants meet eligibility requirements, and that the study is conducted according to the IRB-approve research plan and in accordance with the Federalwide Assurance certification of the site.

Adverse events and serious adverse events are not expected but will be recorded and addressed under institutional procedures.

Documentation and data will be stored and archived in a secure format for at least 2 years and for the duration required by the Sponsor and collaborating sites.

5. Biological Specimens

None are expected to be collected specifically under the Protocol.

## **1. Study Design and Power**

A targeted enrollment of 30 patients is projected as adequate to evaluate the primary endpoint of technical feasibility. Given expected drop-off (up to 66%), a requirement for 30 patients enrolling will lead to expected completion yielding an opportunity to demonstrate both statistical and clinical significance of null hypothesis rejection, with an estimated 10 to 15 patients completing the study.

Based upon a review of published reports of neurostimulation interventions for cognitive dysfunction, a power analysis (observed power  $> 0.8$  at an alpha level of .05) indicates that a sample of 8 participants is sufficient to show a cognitive treatment effect outcomes; such that with large drop-off in the sample, we estimate retained power to measure a medium-large effect size ( $>0.2$ ).

Participants who disenroll during the study period are not expected to specifically be replaced by any procedure other than ongoing recruitment in rolling fashion, until the end of the recruitment period.

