## **2. Analysis Methodology**

Upon completion of the study, a comprehensive analysis will include pre-specified analyses:

- A. Technical Feasibility, or Task Completion, is the primary endpoint and will be evaluated as median reported platform interactions, evaluated at the close of week 8, including range and optional summary statistical measures which may inform distribution or skew of results.
- B. Intervention Usability Rating is a secondary endpoint and will be calculated as whole-number median and range at week 8 of participation, for all subjects. Summary statistical measures will be reported if robustness checks are qualified.
- C. Treatment Progress Measure as assessed by TEA score is a secondary endpoint and will be calculated as whole-number median and range at the close of week 8 of participation (with optional collection without required reporting of scores weekly), for all subjects. Summary statistical measures will be reported if robustness checks are qualified.
- D. Recordation and qualitative assessment of adverse events and actions taken by the investigators in response to AEs or SAEs, per IRB requirements.

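### The power stated in SAP section 1 attaches to no pre-specified analysis: section 2 lists only week-8 medians and ranges, and the effect of 0.2 has no metric

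*SAP*

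**What the plan says.** SAP section 1 (Study Design and Power) first justifies enrolling 30 patients by the primary endpoint of technical feasibility. It allows for drop-off of up to 66%, "with an estimated 10 to 15 patients completing the study", and says this yields an "opportunity to demonstrate both statistical and clinical significance of null hypothesis rejection".

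A separate sentence gives the power statement. "Based upon a review of published reports of neurostimulation interventions for cognitive dysfunction", a power analysis with power above 0.8 at alpha .05 "indicates that a sample of 8 participants is sufficient to show a cognitive treatment effect outcomes". With large drop-off, "we estimate retained power to measure a medium-large effect size", given as above 0.2.

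SAP section 2 (Analysis Methodology) lists the pre-specified analyses:

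- The primary endpoint, task completion, is "evaluated as median reported platform interactions, evaluated at the close of week 8, including range and optional summary statistical measures".
- "Intervention Usability Rating is a secondary endpoint and will be calculated as whole-number median and range at week 8 of participation".
- The TEA score, a treatment progress measure, is a "whole-number median and range at the close of week 8 of participation (with optional collection without required reporting of scores weekly").
- Adverse events are assessed qualitatively.

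For the two secondary endpoints, further summary measures depend on robustness checks that are not defined. Protocol section 2 describes a single-arm feasibility study with weekly assessments. It mentions treatment-related effects as a secondary interest and names no test.

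**The concern.** Power is a property of a test: it needs a hypothesis, a statistic, an alpha with a sidedness, and an effect on a stated scale. Section 1 supplies an alpha, a power and a bare 0.2. Section 2 supplies nothing to which they could apply. A median and range at one time point in one arm, with no null value and no baseline contrast, cannot reject a hypothesis.

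The endpoint does not match either. The power statement concerns a cognitive effect and draws on neurostimulation reports. The intervention is a mobile application, and none of the endpoints in section 2 is labelled cognitive.

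Two misreadings are at stake. A reader could take a week-8 TEA or usability summary as a powered result. Or a test chosen after the data are seen could be presented as if the plan had powered it.

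**Working it through.** **1. Inputs.** From SAP section 1: alpha .05 (sidedness not given), power above 0.8, 8 participants, effect above 0.2 (metric not given), 30 enrolled, drop-off up to 66%, 10 to 15 completers. Not given anywhere: the test, the SD, the number of readings, the within-person correlation.

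**2. The plan's own figures.** Completers: 30 × (1 − 0.66) = 10.2, the lower end of 10 to 15. The upper end, 15/30, is 50% drop-off. This arithmetic is consistent. The figure of 8 participants cannot be reproduced, because no effect size is tied to it. Eight people have 80% power in a two-sided paired t-test for a mean change of 1.16 SD of the change scores, so the figure is not shown to be wrong.

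**3. Tests in section 2.** There are three numeric endpoints, each with a median and range, and no named hypothesis test.

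**4. What 0.2 could mean at 10 and 15 completers.** Metric, number of readings and correlation ρ are my assumptions. Power is at 0.2 exactly; larger effects have more.

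Paired t: noncentrality = 0.2 × √n, with n − 1 df. This is 0.632 for n = 10 and 0.775 for n = 15.

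Within-person F with m readings: λ = f² × n × m / (1 − ρ), with m − 1 and (n − 1)(m − 1) df. For example:

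- Eta-squared 0.2 gives f² = 0.2/0.8 = 0.25. With m = 2 and ρ = 0.5, λ = 0.25 × 10 × 2 / 0.5 = 10 (15 for n = 15).
- Cohen's f of 0.2 gives f² = 0.04. With m = 9 (a baseline and eight weekly readings) and ρ = 0.8, λ = 0.04 × 10 × 9 / 0.2 = 18 (27 for n = 15).

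| Reading of 0.2 | Assumed design | n = 10 | n = 15 |
|---|---|---|---|
| Standardised mean change | paired t, two-sided | 8.8% | 11.2% |
| Standardised mean change | paired t, one-sided | 14.5% | 18.2% |
| Cohen's f | 2 readings, ρ = 0.5 | 20% | 30% |
| Partial eta-squared | 2 readings, λ = f²(n − 1) to f²n | 27–29% | 41–44% |
| Cohen's f | 9 readings, ρ = 0.5 | 39% | 59% |
| f-squared | 2 readings, ρ = 0.5 | 71% | 90% |
| Eta-squared | 2 readings, ρ = 0.5 | 80% | 95% |
| Cohen's f | 9 readings, ρ = 0.8 | 84% | 97% |

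The correlation also matters. For eta-squared with two readings, ρ from 0.3 to 0.7 moves power from 66% to 95% at n = 10 and from 86% to above 99% at n = 15.

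**5. Detectable change if a test were added.** For a two-sided 5% paired t-test, solving for the effect that gives 80% power yields 0.996 SD of the within-person change scores at n = 10, 0.778 at n = 15 and 0.529 at n = 30. The last applies if all enrolled patients are analysed; power at a standardised change of 0.2 is then 18.5%.

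**The case against.** Four points can be made for the plan.

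- **The list may be open.** Section 2 says the comprehensive analysis will include the listed items, and it leaves room for summary measures. This stands in part. A reader might infer that no test will be done, but the text supports only that none is pre-specified. It does not rescue the power claim: the extra measures are optional or conditional, and none names a hypothesis.
- **Section 1 speaks of an opportunity.** A reader might infer that the sponsor promises a statistically significant result. The wording does not go that far, and the power figure stands in a separate sentence about a cognitive effect.
- **The low power depends on one reading.** A reader might take 8.8% to 11.2% as proof that the claim is false. The documents do not support that, since they never say 0.2 is a standardised mean change. Weekly assessments are foreseen, and a repeated-measures reading with nine readings and high correlation would meet the claim. Equally, weekly TEA collection is optional and no repeated-measures model is named.
- **This is a small feasibility study.** That stands, and it lowers the weight of the point. Section 1 justifies the 30 patients by feasibility first, so the power sentence can go without harming the design.

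**Conclusion.** The mismatch between the two SAP sections is real and needs no outside source. Section 1 states an alpha, a power and an effect, and section 2 pre-specifies no analysis to which they apply. The retained-power claim is unsupported and cannot be checked. Across the readings tabulated above, power at 10 to 15 completers runs from about 9% to 97%, and the result turns on assumptions about metric, design and correlation that the SAP does not state. The figure of 8 participants is likewise unsupported, not refuted.

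Severity is minor. What changes is what the trial may claim about statistical significance. The primary endpoint, its analysis and the enrolment target are unaffected.

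**What to change.** Keep 30 enrolled on feasibility grounds. In SAP section 1, delete the wording on an "opportunity to demonstrate both statistical and clinical significance of null hypothesis rejection" and the whole sentence containing "indicates that a sample of 8 participants is sufficient to show a cognitive treatment effect outcomes" and "we estimate retained power to measure a medium-large effect size". Replace with:

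> With drop-off of up to 66%, 30 enrolled patients are expected to give 10 to 15 completers. No hypothesis test is pre-specified; week-8 platform interactions, usability rating and TEA score are described by median and range, and any test added later is exploratory and not powered.

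If the sponsor instead wants to test change in TEA score, section 2 must name the baseline reading, the analysis set and one two-sided 5% test. The analysis set matters because section 2 summarises the secondary endpoints for all subjects, while the expected numbers in section 1 are completers. Section 1 must then give the detectable change for that test. For a paired t-test at 80% power this is about 1.00 SD (n = 10) to 0.78 SD (n = 15) of the within-person change scores in completers, or about 0.53 SD if all 30 are analysed. A rank-based test would suit a score reported as a median, but would need its own figure.

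Cost: SAP wording only, with no extra patients. The stated sensitivity becomes less favourable. The optional test would also require a baseline TEA reading for every participant.

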## **2. Analysis Methodology**

Upon completion of the study, a comprehensive analysis will include pre-specified analyses:

- A. Technical Feasibility, or Task Completion, is the primary endpoint and will be evaluated as median reported platform interactions, evaluated at the close of week 8, including range and optional summary statistical measures which may inform distribution or skew of results.
- B. Intervention Usability Rating is a secondary endpoint and will be calculated as whole-number median and range at week 8 of participation, for all subjects. Summary statistical measures will be reported if robustness checks are qualified.
- C. Treatment Progress Measure as assessed by TEA score is a secondary endpoint and will be calculated as whole-number median and range at the close of week 8 of participation (with optional collection without required reporting of scores weekly), for all subjects. Summary statistical measures will be reported if robustness checks are qualified.
- D. Recordation and qualitative assessment of adverse events and actions taken by the investigators in response to AEs or SAEs, per IRB requirements.

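### TEA treatment progress is summarised only as a week-8 level in an expected 10 to 15 of 30 participants, with no required entry or weekly score and no rule for missing scores

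*SAP*

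**What the plan says.** SAP section 2, item C makes the TEA score a secondary endpoint and the study's measure of treatment progress. It "will be calculated as whole-number median and range at the close of week 8 of participation", and this is to be done "for all subjects". Weekly scores are covered by one clause: "with optional collection without required reporting of scores weekly". Further summary statistics depend on robustness checks that are not described.

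Protocol section 2 asks participants to use the platform for at least 8 weeks, "in addition to completing weekly assessments". It does not list those assessments and does not mention TEA.

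SAP section 1 sets enrolment at 30, allows for drop-off of up to 66%, and plans "with an estimated 10 to 15 patients completing the study". On replacement it says: "Participants who disenroll during the study period are not expected to specifically be replaced by any procedure other than ongoing recruitment in rolling fashion".

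The supplied text does not require a TEA score at entry. It has no analysis of change, no rule for a participant without a week-8 score, and no comparison of completers with leavers.

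**The concern.** A measure of progress needs a starting point. Item C gives a level at one time, so even with complete data it could not show whether anyone improved. The data will also not be complete, because the SAP itself expects half to two thirds of participants to be gone by week 8.

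If leavers differ from stayers on TEA, the week-8 median describes a selected group under a label that covers everyone. Drop-out causes the loss of week-8 scores. The optional clause decides whether anything is left to work with. If entry and weekly scores exist, change can be estimated and leavers can be compared with completers. If they were never collected, no later analysis can supply them.

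**Working it through.** **1. The plan's own figure.** Inputs from SAP section 1: 30 enrolled, drop-off up to 66%, 10 to 15 completing.

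- Completers = N × (1 − d). At d = 0.66: 30 × 0.34 = 10.2. At d = 0.50: 30 × 0.50 = 15.
- In reverse: 1 − 10/30 = 66.7% and 1 − 15/30 = 50%.

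The SAP's 10 to 15 is reproduced. The 66% is stated as an upper limit; the 50% is not stated and follows from 15/30. Without follow-up of leavers, 30 − 15 = 15 to 30 − 10 = 20 participants would have no week-8 TEA score.

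**2. What the passages allow.** Item C claims a summary for everyone, section 1 expects week-8 data from a third to a half, and no rule connects the two. That the result rests on completers is therefore an inference from the missing rule. The SAP does not define a completer set.

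**3. How far the median could move.** The documents give no TEA scale, direction, SD or drop-out mechanism, so this is an illustration only. Assumptions: TEA in SD units with higher meaning better, no true change, within-person correlation 0.6, and 34% or 50% retained at week 8. The log-odds of leaving each week rise by a fixed slope per SD of worse previous score. Shift of the completers' week-8 median from the median of all enrolled, in SD:

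| Log-odds slope | 34% retained | 50% retained |
|---|---|---|
| 0 | 0.00 | 0.00 |
| 0.25 | 0.15 | 0.09 |
| 0.5 | 0.28 | 0.18 to 0.19 |
| 1.0 | 0.46 | 0.32 |

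If better scorers leave instead (slope 0.5), the shift is about −0.29 to −0.18 SD.

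A cross-check used a different model: 30 enrolled, the top 10 or 15 retained on a variable correlated ρ with the week-8 score, 40,000 simulated trials. For ρ = 0, 0.2, 0.3 and 0.5, the shift is 0.003, 0.214, 0.319 and 0.529 SD with 10 completers, and 0.001, 0.155, 0.231 and 0.382 SD with 15.

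**4. What repairs it.**

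- In the set-up of step 3, completers' mean change from their own entry score is within about 0.04 SD of the truth. That uses two time points and no weekly scores.
- If individual courses differ strongly (true change over the 8 weeks varying between people with SD 1.0), completers' change is itself off by 0.06 to 0.28 SD for slopes 0.25 to 1.0. Weekly scores from leavers then carry information that entry and week-8 scores do not.
- A mixed model on all weekly scores had bias of 0.02 SD or less when leaving depended only on observed scores. When leaving depended on the current, unobserved score (slope 0.5 to 1.0), its bias in change was about 0.04 to 0.13 SD.

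**The case against.** The strongest defence is proportion. TEA is a descriptive secondary endpoint with no planned test, in a single-arm feasibility study whose primary endpoint is platform interactions. A mixed model for about 30 people can look like a reviewer's preference, and a missing-data statement with the number contributing might be enough. This stands in part: it limits the consequence, and the exact model is a matter of choice. It does not excuse a progress measure without a starting value. SAP section 1 also claims power for a cognitive treatment effect, although it does not tie that to TEA, so outcome data are likely to be interpreted.

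A reader might also infer more than the documents support:

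- *That the Protocol and SAP contradict each other.* The Protocol requests weekly assessments without naming them, and the SAP permits weekly TEA. Both can hold. This is an ambiguity to reconcile.
- *That weekly scores will be withheld or thrown away.* The SAP says only that reporting them is not required.
- *That the week-8 median is biased and flatters the intervention.* This needs leaving to be related to TEA, in a known direction. The documents give neither. The shift is zero without that link, and its sign can reverse.
- *That the optional weekly clause causes the bias.* In the illustration most of the shift comes from summarising a level without an entry score.
- *That the shift exceeds the effect of 0.2 named in SAP section 1.* The SAP gives no unit for that figure, so the comparison holds only if it is in SD units.

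**Conclusion.** The point holds as a gap in design and analysis. As written, item C yields a week-8 level that cannot show progress. Unless leavers are still assessed, it will come from about 10 to 15 of 30 participants. The risk of bias is real, but its size and direction are unknown. The illustrative range is 0 SD with no dependence and about 0.09 to 0.46 SD at log-odds slopes of 0.25 to 1.0, under the assumptions listed above, with the sign reversed if better scorers leave. The missing entry score is the main defect. Optional weekly collection is the second, and matters more the more individual courses differ. The change should be made before data collection, because uncollected scores cannot be recovered. It does not affect the primary endpoint.

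**What to change.** In item C, replace the optional clause with: *TEA is collected at entry and at each weekly assessment through week 8 for all enrolled participants.* Then:

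- Make change from entry to week 8 the TEA summary, using all available scores. A simple mixed model would do, with its missing-at-random assumption stated.
- Show the week-8 median and range beside it, with the number contributing.
- State how a missing week-8 score is handled, and whether people who leave are still asked for one.
- Tabulate entry and last observed TEA by completer or leaver.
- In Protocol section 2, name the weekly assessments and say whether TEA is one of them, so that the two documents agree.

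The cost is some extra assessment time each week, which cannot be quantified because TEA's length is not given, and a little more analysis. Participants are already asked for weekly assessments. The mixed model does not remove bias if leaving depends on scores that were never observed, so the completer and leaver table should be read with it.
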